#### **6.1.2. Analysis of the Primary Efficacy Endpoint**

The primary analysis of PFS will be performed using the Kaplan-Meier (KM) method based on IRC response assessments for the FAS. Medians, Q1, Q3 of the PFS distributions, and the proportion of subjects who are progression-free at Week 16 (for CLL after BCR targeted therapy, MCL, and DLBCL) and Week 24 (for CLL and iNHL) from the first dosing date will be

provided along with corresponding 95% confidence intervals (CIs). The loglog transformation will be used to compute the CIs.

PFS rate of the CLL prior BTK inhibitor exposure and CLL prior PI3K inhibitor exposure cohorts will be estimated separately. PFS rate of the CLL dose ranging cohort will be estimated by dose levels.

## **6.2. Secondary Efficacy Endpoint**

### **6.2.1. Definition of Secondary Efficacy Endpoints**

Same as the primary efficacy endpoint analysis, the response assessments by IRC will be used for the secondary efficacy endpoints' analyses based on the FAS. The response assessments after other anti-cancer therapy (if they are available) won't be included for secondary efficacy endpoints analyses.

- Objective response rate (ORR).

Best overall response (BOR) of complete response (CR), partial response (PR), stable disease (SD), progressive disease (PD), not evaluable (NE), no disease (ND), and not applicable (NA) is allowed. For subjects with LPL/WM, a very good partial response (VGPR) or minor response (MR) is also allowed. Again, a single PD determination followed by a determination that indicated either no change or improvement in disease prior to the single PD observation will not be considered as PD.

ORR is defined as the proportion of subjects with BOR during ENTO therapy of CR or PR (or VGPR or MR for subjects with LPL/WM). Subjects who do not have sufficient baseline tumor assessment, whose on-study tumor status information is not adequate for response status assessment or who received new anti-cancer therapy prior to achieving CR or PR (or VGPR or MR for subjects with LPL/WM), will be considered as non-responders.

- Duration of response (DOR).

DOR is defined as the interval from the first time when the objective response (CR or PR [or VGPR or MR for subjects with LPL/WM]) is achieved to the earlier of the first documentation of definitive disease progression or death from any cause.

- Time to response (TTR).

TTR is defined as the interval from the first dose of ENTO to the first time when the response (CR or PR [or VGPR or MR for subjects with LPL/WM]) is achieved.

## **6.2.2. Analysis Methods for Secondary Efficacy Endpoints**

### **6.2.2.1. Objective Response Rate**

ORR and 95% CIs will be summarized. The number and proportion of subjects whose best overall response were evaluated as CR, PR, VGPR, MR, SD, PD, NE, ND, and NA will also be tabulated.

Both IRC and investigator's response assessments will be presented in by-subject listings.

### **6.2.2.2. Duration of Response**

DOR analysis will be conducted in the responding subjects of FAS set. Responding subjects are those who achieve a CR or PR (or VGPR/MR for LPL/WM subjects). The censoring rule is same as PFS analyses (see [Appendix 2](#)).

DOR will be summarized using the KM method. The KM estimates of the DOR survival function will be presented. The median of DOR will be provided along with the corresponding 95% CIs. Additionally, the Q1 and Q3 will also be provided. The log-log transformation will be used to compute the CIs.

### **6.2.2.3. Time to Response**

TTR analysis will be conducted in the responding subjects in FAS. Responding subjects are those who achieve a CR or PR (or VGPR/MR for LPL/WM subjects). TTR will be summarized using descriptive statistics.

## **6.3. Changes from Protocol-Specified Efficacy Analyses**

The study final CSR is determined in synoptic version. The sensitivity analyses will not be performed.

## **7. SAFETY ANALYSES**

### **7.1. Adverse Events and Deaths**

#### **7.1.1. Adverse Event Dictionary**

Clinical and laboratory adverse events (AEs) will be coded using the current version of MedDRA. System organ class (SOC), high-level group term (HLGT), high-level term (HLT), preferred term (PT), and lower-level term (LLT) will be provided in the AE dataset.

#### **7.1.2. Adverse Event Severity**

Adverse events are graded by the investigator as Grade 1, 2, 3, 4, or 5 according to CTCAE Version 4.03 {U.S. Department of Health and Human Services 2010}. The severity grade of events for which the investigator did not record severity will be categorized as “missing” for tabular summaries and data listings. The missing category will be listed last in summary presentation.

Severity of adverse events will be determined by the investigator as mild, moderate, or severe. The severity of events for which the investigator did not record severity will be categorized as “missing” for tabular summaries and data listings. The missing category will be listed last in summary presentation.

#### **7.1.3. Relationship of Adverse Events to Study Drug**

Related AEs are those for which the investigator selected “Related” on the AE CRF to the question of “Related to Study Treatment.” Relatedness will always default to the investigator’s choice, not that of the medical monitor. Events for which the investigator did not record relationship to study drug will be considered related to study drug for summary purposes. However, by-subject data listings will show the relationship as missing.

#### **7.1.4. Serious Adverse Events**

Serious adverse events (SAEs) will be identified and captured as SAEs if the AEs met the definitions of SAEs that were specified in the study protocol. SAEs captured and stored in the clinical database will be reconciled with the SAE database from the Gilead Pharmacovigilance and Epidemiology Department before data finalization.

#### **7.1.5. Treatment-Emergent Adverse Events**

##### **7.1.5.1. Definition of Treatment-Emergent Adverse Events**

Treatment-emergent adverse events (TEAEs) are defined as 1 or both of the following:

- Any AEs with an onset date on or after the study drug start date and no later than 30 days after permanent discontinuation of study drug

- Any AEs leading to premature discontinuation of study drug.

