7. ADVERSE EVENTS AND TOXICITY MANAGEMENT

7.1. Adverse Events

An adverse event (AE) is any untoward medical occurrence in a clinical investigation subject administered a medicinal product and which does not necessarily have a causal relationship with this treatment. An AE can therefore be any unfavorable and unintended sign, symptom, or disease temporally associated with the use of a medicinal product, whether or not considered related to the medicinal product.

AEs also include the following:

- All AEs that occur from the signing of the informed consent onwards and throughout the duration of the study, including the 30-day follow-up off-study period.
- Pre- or post-treatment complications that occur as a result of a protocol-mandated procedure (eg, venipuncture or biopsy) during or after screening (before the administration of study investigational medicinal product)
- Any pre-existing condition that increases in severity, or changes in nature during or as a consequence of the study investigational medicinal product phase of this trial, will also be considered an AE
- Complications and termination of pregnancy

An AE does not include the following:

- Medical or surgical procedures (eg, surgery, endoscopy, tooth extraction, transfusion) performed; the condition that led to the procedure may be an AE if applicable
- Pre-existing diseases or conditions or laboratory abnormalities present or detected before the screening visit that do not worsen
- Situations where an untoward medical occurrence has not occurred (eg, hospitalization for elective surgery, social and/or convenience admissions)
- Overdose without clinical sequelae (see Section 7.7)
- Any medical condition or clinically significant laboratory abnormality with an onset date before the consent form is signed. It is considered to be pre-existing and should be documented on the medical history eCRF
- Uncomplicated pregnancy
- An induced elective abortion to terminate a pregnancy without medical reason

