7.7. Special Situation Reports

Special situation reports include pregnancy reports, reports of medication error, abuse, misuse, or overdose, and reports of adverse reactions associated with product complaints.

A pregnancy report is used to report pregnancies following maternal or paternal exposure to the product.

Medication error is any unintentional error in the prescribing, dispensing, or administration of a medicinal product while in the control of the health care provider, subject, or consumer.

Abuse is defined as persistent or sporadic intentional excessive use of a medicinal product by a subject.

Misuse is defined as any intentional or inappropriate use of a medicinal product that is not in accordance with the protocol instructions or the local prescribing information.

An overdose is defined as an accidental or intentional administration of a quantity of a medicinal product given per administration or cumulatively which is above the maximum recommended dose as per protocol or in the product labelling (as it applies to the daily dose of the subject in question).

In cases of a discrepancy in drug accountability, overdose will be established only when it is clear that the subject has taken the excess dose(s) or the investigator has reason to suspect that the subject has taken the additional dose(s).

Product complaint is defined as any written or verbal report arising from potential deviations in the manufacture, packaging or distribution of the product.

Instructions for reporting Special Situation Reports are described in Section [7.8.1](#)

7.8. Investigator Requirements and Instructions for Reporting Adverse Events and Serious Adverse Events to Gilead

All SAEs, regardless of cause or relationship, that occur after the subject first consents to participate in the study (ie, signing the informed consent) and throughout the duration of the study, including the protocol-required post treatment follow-up period, must be reported to the CRF/eCRF database and Gilead Drug Safety and Public Health (DSPH) as instructed. This also includes any SAEs resulting from protocol-associated procedures performed from screening onwards.

All AEs, regardless of cause or relationship, that occur from initiation of study medication until 4 weeks after last administration of study IMP must be reported to the CRF/eCRF database as instructed.

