8.5.3.3. Adverse Events

All AEs will be listed. The focus of AE summarization will be on treatment-emergent AEs. A treatment-emergent AE is defined as an AE that occurs or worsens in the period from the first dose of study treatment to 30 days after the last dose of study treatment. Adverse events that occur before the first dose of study treatment or > 30 days after the subject is discontinued from study treatment will be included in data listings.

Adverse events will be classified using the Medical Dictionary for Regulatory Activities (MedDRA) (<http://www.meddramsso.com>) with descriptions by System Organ Class, High-Level Group Term, High-Level Term, Preferred Term, and Lower-Level Term. The severity of AEs will be graded by the investigator according to the CTCAE, Version 4.03 whenever possible. If a CTCAE criterion does not exist for a specific type of AE, the grade corresponding to the appropriate adjective will be used by the investigator to describe the maximum intensity of the AE: Grade 1 (mild), Grade 2 (moderate), Grade 3 (severe), Grade 4 (life threatening), or Grade 5 (fatal). The relationship of the AE to the study drug will be categorized as related or unrelated.

Treatment-emergent AEs will be summarized. Summary tables will be presented to show the number of subjects reporting treatment-emergent AEs by severity grade and corresponding percentages. A subject who reports multiple treatment-emergent AEs within the same Preferred Term (or System Organ Class) is counted only once for that Preferred Term (or System Organ Class) using the worst severity grade. Adverse event descriptions will be presented in alphabetical order of System Organ Class, then by decreasing frequency in the “overall” column for a given Preferred Term.

Separate listings and summaries will be prepared for the following types of treatment-emergent AEs:

- Study-drug-related AEs
- AEs that are Grade ≥ 3 in severity
- AEs leading to study drug interruption and/or dose modification
- AEs leading to study drug discontinuation
- SAEs (with categorization of the primary reason that the AE is considered serious, eg, death, hospitalization, etc)

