#### **7.7. Changes from Protocol-Specified Safety Analyses**

There are no deviations from the protocol-specified safety analyses.

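### SAP 7.1.5.1 omits the worsening criterion in the protocol's definition of a treatment-emergent AE and SAP 7.7 declares no change, so TEAE counts may be understated

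*SAP*

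**What the plan says.** Protocol 8.5.3.3 defines a treatment-emergent AE as "an AE that occurs or worsens in the period from the first dose of study treatment to 30 days after the last dose". It has two routes: new occurrence and worsening.

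SAP 7.1.5.1 also has two routes, but not the same two. The first is by date: "Any AEs with an onset date on or after the study drug start date", ending 30 days after permanent discontinuation. The second is by consequence: "Any AEs leading to premature discontinuation of study drug". Neither refers to a change in severity.

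SAP 7.7, the section reserved for changes to the safety analyses, says: "There are no deviations from the protocol-specified safety analyses".

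On collection, protocol 7.1 counts as AEs "All AEs that occur from the signing of the informed consent onwards". Protocol 6.2.1 and footnote f of the schedule of assessments (protocol Appendix 2, repeated in SAP Appendix 1) agree with it. Protocol 7.8 instead asks for reporting to the eCRF of "All AEs, regardless of cause or relationship, that occur from initiation of study medication until 4 weeks after last administration of study IMP", while requiring SAEs from consent.

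**The concern.** The two documents define the main safety variable differently, and the section where a reader would look for the difference denies that there is one. SAP 6.3 does declare its change to the efficacy analyses, so a reader has reason to trust 7.7.

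Safety and tolerability is a secondary objective, and the report is to be synoptic, so the TEAE tables carry much of the safety message. Most cohorts have a single arm, so no comparator would share the effect of a narrower definition. The SAP gives no reason for treating clinical AEs this way. For laboratory abnormalities, SAP 7.2.1.1 keeps a worsening rule (at least one grade above baseline), in line with protocol 8.5.3.4.

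**Working it through.** No power, alpha or sample-size figure is involved, so the check is a comparison of text.

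**1. Does another SAP rule restore the missing criterion?** No. SAP 7.1.5.2 (incomplete dates) works only from onset and stop dates. The maximum-severity rule in SAP 7.1.6.1 applies within events already classed as treatment-emergent.

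**2. Which events are exposed?** Take an AE that worsens between first dose and 30 days after last dose. All of these count under the protocol. Under the SAP:

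- The condition was present before consent. Protocol 7.1 puts it in medical history and makes an AE of "Any pre-existing condition that increases in severity, or changes in nature during or as a consequence of the study investigational medicinal product phase". If the worsening date is entered as the onset, the SAP counts it.
- Onset lies between consent and first dose, and the worsening is entered as a new AE with its own onset date: counted.
- Onset lies between consent and first dose, the worsening stays in the same record, and the AE leads to discontinuation: counted by the second route.
- Onset lies between consent and first dose, the worsening stays in the same record, and the AE does not lead to discontinuation: **not counted**.

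Only the last case is lost by the SAP's own wording. Its window is the screening period, up to 35 days before Cycle 1 Day 1 (protocol 6.2.1).

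**3. Can such a record be in the database?** For SAEs, yes: protocol 7.8 requires them from consent. For non-serious AEs it depends on which instruction sites followed. Protocol 7.1, 6.2.1 and footnote f say from consent; 7.8 says from first study medication.

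**4. Which outputs are affected?** SAP 7.1.6.1 builds its AE incidence tables on the TEAE flag: all TEAEs, Grade 3 or higher, related, serious, leading to death, interruption or reduction. A lost event would appear only in listings, marked as not treatment-emergent. The table of TEAEs leading to discontinuation is protected by the second route. Laboratory abnormality tables are unaffected.

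**5. How large is it?** The documents give no count of screening-onset AEs that worsened and no eCRF rule for dating a worsening. The number lost lies between zero (every worsening is a new AE) and all worsened screening-onset AEs that did not lead to discontinuation (every worsening stays in its original record). As a scale only, one lost subject moves a table row by at most 1/40 = 2.5 percentage points in a column of 40 subjects, and by 1/20 = 5 points in a column of 20. These are the planned maxima in protocol 8.7 for most cohorts, and for the Richter's sub-cohorts and each dose-ranging level, respectively.

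**The case against.** The best defence is that the onset rule may already deliver the protocol's definition. If sites open a new AE whenever a condition worsens, nothing is lost. For conditions present before consent the protocol points that way: they belong in medical history, their worsening is an AE, and protocol 6.9.2 sends clinically significant deterioration from the screening examination to the AE page. This stands. A reader might infer that disease symptoms common before treatment, such as fatigue or fever, drop out of the tables generally. The documents do not support that, because symptoms already present at consent have no earlier AE record to carry a pre-dose onset. Cytopenias are a weak example too: laboratory abnormalities are usually not recorded as AEs (protocol 7.9), and the laboratory tables keep the worsening rule.

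The defence does not cover AEs that start after consent and before dosing. They are not pre-existing in the protocol's sense, and no passage requires a new record or a new onset date when they worsen.

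It can also be said that non-serious screening AEs may never have been collected. Under protocol 7.8 that is possible, but other sections of the protocol and the SAP's own schedule say otherwise, and SAEs are collected from consent on either reading.

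Finally, the safety analysis is descriptive, with no comparison or decision rule, and all AEs, SAEs and deaths are listed. That limits the harm. It does not make the statement in SAP 7.7 correct.

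**Conclusion.** The SAP omits the worsening criterion of protocol 8.5.3.3, and SAP 7.7 is wrong to say that nothing has changed. Both follow from the text alone.

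The effect on results is conditional. TEAE counts, including Grade 3 or higher and serious, may be understated for AEs that start between consent and first dose, worsen on drug within one record and do not lead to discontinuation. This rests on such AEs having been collected and on worsening having been kept in the original record. The documents settle neither, except that SAEs are to be collected from consent.

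A reader might go further and conclude that the counts are understated, or attach a percentage. Neither is supported: zero is a possible value, and no figure in the documents bears on the frequency. The net direction for total TEAEs against the protocol definition is also open. The SAP's second route has no date condition, so it can admit an AE that began before dosing and led to stopping without any increase in grade. SAP 7.1.5.2 also treats a missing onset date as treatment-emergent in several situations.

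The point should be corrected before the SAP is finalized. It does not put the trial's main conclusions in doubt.

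**What to change.** Add a third criterion to SAP 7.1.5.1: *or any AE with onset before first dose that increases in CTCAE grade on or after first dose and no later than 30 days after last dose*. State how a grade increase is identified and dated: by a new AE record at worsening, or by a site query where only one record exists. The documents do not show that the eCRF holds dated grade changes, so the derivation should not presume it.

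If the sponsor prefers the onset-only rule, declare it in SAP 7.7 as a change from protocol 8.5.3.3 and give the reason.

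Reconcile the start of AE collection between protocol 7.1 and 6.2.1 (consent) and protocol 7.8 (first study medication for non-serious AEs), and say which applied to the data in hand.

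The cost is one sentence in the SAP, a derivation step and possibly a few site queries. SAP section 1 places finalization of the SAP before that of the database, so the change can be made in time.

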#### 7.1.5.2. Incomplete Dates

If the onset date of the AE is incomplete and the AE stop date is not prior to the first dosing date of study drug, then the month and year (or year alone if month is not recorded) of onset determine whether an AE is treatment emergent. The event is considered treatment emergent if both of the following 2 criteria are met:

- The AE onset is the same as or after the month and year (or year) of the first dosing date of study drug, and
- The AE onset date is the same as or before the month and year (or year) of the date corresponding to 30 days after the date of the last dose of study drug

An AE with completely missing onset and stop dates, or with the onset date missing and a stop date later than the first dosing date of study drug, will be considered to be treatment emergent. In addition, an AE with the onset date missing and incomplete stop date with the same or later month and year (or year alone if month is not recorded) as the first dosing date of study drug will be considered treatment emergent.

In case when the AE onset date is incomplete and needs to be imputed, the following algorithm will be followed:

- If the day is missing but the month and year are available, then the imputed day will be the first day of the month or the first dosing date if they have the same month and year, whichever is later.
- If the day and month are missing but year is available, then the imputed day and month will be 01Jan or the first dosing date if they have the same year, whichever is later.

#### 7.1.6. Summaries of Adverse Events and Deaths

Treatment-emergent AEs will be summarized based on the Safety Analysis Set.

##### 7.1.6.1. Summaries of AE Incidence by Severity

The number and percentage of subjects who experienced at least 1 TEAE will be provided and summarized by SOC, and PT. For the AE categories described below, summaries will be provided by SOC, PT, and maximum severity (if applicable):

- TEAEs
- TEAEs of Grade 3 or higher
- TE treatment-related AEs
- TE Treatment-related AEs with Grade 3 or higher

- TE SAEs
- TE treatment-related SAEs
- TEAEs leading to discontinuation of study drug
- TEAEs leading to death
- TEAEs leading to dose interruption of study drug
- TEAEs leading to dose reduction of study drug

A brief, high-level summary of AEs described above will be provided by treatment group and by the number and percentage of subjects who experienced the above AEs.

Multiple events will be counted only once per subject in each summary. Adverse events will be summarized and listed first in alphabetic order of SOC and then by PT in descending order of total frequency within each SOC. For summaries by severity, the most severe severity will be used for those AEs that occurred more than once in a given subject during the study.

In addition to the above summary tables, TEAEs, TEAEs of Grade 3 or higher, TE treatment-related AEs, and TE SAEs will be summarized by PT only in descending order of total frequency.

In addition, data listings will be provided for the following:

- All AEs, indicating whether the event is treatment emergent
- All SAEs
- Deaths
- All AEs leading to death
- All AEs leading to discontinuation of study drug
- All AEs leading to dose interruption of study drug
- All AEs leading to dose reduction of study drug

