3.1.2. CLL Dose Ranging Cohort

[figure not shown]
For the CLL dose ranging cohort, subjects enrolled will be randomized 1:1:1 to receive 100 mg, 200 mg or 400 mg (200 mg x 2) of GS-9973 SDD BID. Therefore 20 subjects are treated at each of the three dose levels.

Because the CLL dose ranging cohort consists of 3 different dose levels each with approximately 20 subjects, the continuation data review of futility will not be conducted for this cohort.

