5.3.6. Management of Dose Limiting Toxicities

Adverse events and laboratory abnormalities will be graded using the CTCAE, Version 4.03. Dose modification of GS-9973/GS-9973 SDD should be performed for the following dose limiting AEs:

- Grade 4 hematological toxicities persisting for ≥ 14 days
- Grade ≥ 3 toxicities of other types

Of note, the occurrence of asymptomatic lymphocytosis will not be considered a toxicity requiring dose modification. Dose reduction will not be required for untreated vomiting, diarrhea, or constipation; interruption of dosing until these symptoms are adequately treated is permitted.

Table 5-2. GS-9973 MM Dose Levels

Dose Level	GS-9973 MM Dose (mg BID fasting)
0	800
-1	600
-2	400
-3	200

Table 5-3. GS-9973 SDD Dose Levels

Dose Level	GS-9973 SDD Dose (mg BID fasting)
CLL Prior BTK inhibitor Exposure, CLL Prior PI3K inhibitor Exposure or CLL Dose Ranging randomized to 400mg BID or Dose level 0	400
CLL Dose Ranging randomized to 200mg BID or Dose level -1	200
CLL Dose Ranging randomized to 100mg BID or Dose level -2	100

If a subject experiences an AE or laboratory abnormality that is suspected to be related to GS-9973/GS-9973 SDD, and requires a dose reduction, GS-9973/GS-9973 SDD administration should be interrupted, as necessary, until the AE or laboratory abnormality resolves or stabilizes to an acceptable degree (generally to Grade 1 or the pretreatment severity grade, whichever is higher). More frequent monitoring (eg, once per week) may be warranted until adverse events or laboratory abnormalities are clearly improving. When treatment is reinstated, the dose of GS-9973/GS-9973 SDD should be reduced by 1 dose level (see [Table 5-2](#) and [Table 5-3](#)).

Successive adjustments to progressively lower dose levels can be made. If the subject cannot tolerate GS-9973/GS-9973 SDD at the lowest dose level then the subject should discontinue GS-9973/GS-9973 SDD therapy.

After a dose is reduced, the dose need not be re-escalated, even if there is minimal or no toxicity with the reduced dose. However, if the subject tolerates a reduced dose of GS-9973/GS-9973 SDD for ≥ 4 weeks then the GS-9973/GS-9973 SDD dose may be increased to the next higher dose level, at the discretion of the investigator. Such re-escalation should strongly be considered if further evaluation reveals that the AE that led to the dose reduction was not GS-9973/GS-9973

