8.7. Power and Sample Size Calculation

This study comprises of multiple cohorts. The planned sample size for CLL, FL, DLBCL, MCL is from 10 up to 40 each cohort; for the cohort of LPL, SLL and MZL is 45; for the CLL BCR targeted therapy cohort (CLL prior BTK inhibitor exposure and CLL prior PI3K inhibitor exposure, respectively) is from 20 up to 60 (up to 20 for subjects experiencing Richter's transformation and up to 40 for those without experiencing Richter's transformation); for the CLL dose ranging cohort is 60 (20 at each dose level). The total sample size is from 185 up to 385.

Given a Beta(0.5, 1.5) prior and a sample size of 40 subjects per cohort [Table 8-1](#) shows the posterior mean and 95% credible interval for response rate after observing response rate ranging from 0.1 to 0.65.

Given the same prior and a sample size of 20 subjects for the CLL subjects experiencing Richter's transformation after BCR targeted therapy, [Table 8-2](#) shows the posterior mean and 95% credible interval for response rate after observing response rate ranging from 0.1 to 0.65.

Table 8-1. Estimated Posterior Mean and 95% Credible Interval of Response Rate with Sample Size = 40

Observed Response Rate	Posterior Mean	95% Credible Interval
0.10	0.107	(0.034, 0.215)
0.20	0.202	(0.097, 0.335)
0.30	0.297	(0.171, 0.442)
0.40	0.393	(0.253, 0.543)
0.50	0.488	(0.340, 0.637)
0.60	0.583	(0.433, 0.726)
0.65	0.631	(0.482, 0.769)

Table 8-2. Estimated Posterior Mean and 95% Credible Interval of Response Rate with Sample Size = 20

Observed Response Rate	Posterior Mean	95% Credible Interval
0.10	0.114	(0.020, 0.272)
0.20	0.205	(0.068, 0.392)
0.30	0.295	(0.129, 0.497)
0.40	0.386	(0.199, 0.593)
0.50	0.477	(0.277, 0.681)
0.60	0.568	(0.362, 0.763)
0.65	0.614	(0.407, 0.801)

With the decision rule employed in this study and assuming enrollment is terminated once the futility criterion is met, for a given true response rate within a malignancy, [Table 8-3](#) shows the probability of claiming futility and the sample size needed to claim futility for this design, which is based on 10,000 simulations. When the true response rate is low (0.1), this design has a high probability (~84%) of claiming futility and when the true response rate is high (0.5), this design has a low probability (0.15%) of claiming futility.

Table 8-3. Probability and Sample Size of Claiming a Futility by the End of Study Using Futility Criteria $\Pr(\theta < 0.2 | \text{data}) > 0.9$

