**Table 3-2. Subject Grouping for the CLL Dose Ranging Cohort**

100mg BID N = xx	200mg BID N = xx	400mg BID N = xx	Total N=xx
xx	xx	xx	xx

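### In the CLL dose-ranging cohort, separate summaries of TEAEs leading to dose reduction and to discontinuation do not compare tolerability fairly, because the arms start with two, one and no lower dose levels

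*SAP*

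**What the plan says.** Subjects in this cohort are "randomized 1:1:1 to receive 100 mg, 200 mg or 400 mg (200 mg x 2) of GS-9973 SDD BID" (Protocol 3.1.2). Protocol Table 5-3 lists three SDD levels, 400, 200 and 100 mg BID. The last row reads "CLL Dose Ranging randomized to 100mg BID or Dose level -2", so the 100 mg arm starts on the lowest level.

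For a toxicity that requires a reduction, Protocol 5.3.6 states: "When treatment is reinstated, the dose of GS-9973/GS-9973 SDD should be reduced by 1 dose level". At the bottom of the table: "If the subject cannot tolerate GS-9973/GS-9973 SDD at the lowest dose level then the subject should discontinue GS-9973/GS-9973 SDD therapy".

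SAP 7.1.6.1 lists "TEAEs leading to discontinuation of study drug" and "TEAEs leading to dose reduction of study drug" as separate categories, with dose interruption as a third. The columns are those of SAP Table 3-2, "Subject Grouping for the CLL Dose Ranging Cohort": 100, 200 and 400 mg BID and a total. No category combines these actions, and no note mentions the different number of lower levels. Protocol 8.5.3.3 had planned a grouped category of interruption and/or dose modification; the SAP splits it.

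**The concern.** A subject who needs a lower dose can appear in the reduction row when starting at 400 or 200 mg. The same subject starting at 100 mg cannot, and may appear in the discontinuation row instead. The division between the two rows therefore reflects partly how toxic the dose is and partly how many levels lie below it. A reader comparing columns could take the lowest dose to be the worst tolerated on discontinuation and the best tolerated on reduction when toxicity is the same.

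This matters because safety and tolerability are a secondary objective (Protocol 2.1), Protocol 1.6.2 names the safety profile among the things that lower-dose exploration should evaluate, and this is the study's only randomised comparison.

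**Working it through.** **The plan's own figure.** Protocol 8.7 gives the size as "for the CLL dose ranging cohort is 60 (20 at each dose level"). Three arms x 20 = 60, which agrees. The documents give no toxicity rate, power or alpha for this cohort, so what follows is an illustration of expected counts.

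**Inputs**
- n = 20 per arm (Protocol 8.7).
- Lower levels available: two at 400 mg, one at 200 mg, none at 100 mg (Protocol Table 5-3).
- p, the probability of a toxicity that calls for a step down, set equal in all arms. The nearest figure in the documents is Grade 3 or 4 transaminase elevation in 11/109 = 10.1% (Protocol 1.7.1), seen with the MM formulation and not in these arms. The values 25% and 40% are assumed.
- q, the probability that the toxicity recurs at each lower level: assumed 0.5, range 0.25 to 0.75.
- s, the share resumed at the same level after interruption: assumed 0 or 0.5.

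**Formulas**, before any escalation
- Reductions: 20p(1-s) at 400 and at 200 mg; 0 at 100 mg.
- Discontinuations: 20p(1-s)q² at 400 mg, 20p(1-s)q at 200 mg, 20p(1-s) at 100 mg.

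**Results** with s = 0 and q = 0.5, expected subjects of 20 at 400/200/100 mg

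| p | Reductions | Discontinuations |
|---|---|---|
| 10.1% | 2.0 / 2.0 / 0 | 0.5 / 1.0 / 2.0 |
| 25% | 5.0 / 5.0 / 0 | 1.25 / 2.5 / 5.0 |
| 40% | 8.0 / 8.0 / 0 | 2.0 / 4.0 / 8.0 |

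For p = 25% the discontinuations are 20 x 0.25 x 0.5² = 1.25, 20 x 0.25 x 0.5 = 2.5 and 20 x 0.25 = 5.0. Over q = 0.25 to 0.75 they run from 0.3 to 2.8 at 400 mg and from 1.25 to 3.75 at 200 mg, and stay at 5.0 at 100 mg. With s = 0.5 every count halves and the ordering stays.

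**Escalation.** The Protocol Synopsis (Study Design) lets subjects on lower SDD doses go up to 400 mg BID after 8 weeks or at progression, under stated conditions. If a share e of the 100 mg subjects with no earlier step-down toxicity is escalated and then faces the same p, expected reductions in that arm are 20(1-p)ep. For p = 25% this is 20 x 0.75 x 0.25 x 0.25 = 0.94 at e = 25% and 1.88 at e = 50%. The chance of at least one, 1-(1-(1-p)ep)^20, is 0.617 and 0.860. For p = 10.1% the expected numbers are 0.45 and 0.91, and the chances 0.368 and 0.605.

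**Which combined row.** Suppose p = 25% and half of the 100 mg subjects with such a toxicity resume at 100 mg, while the other arms always step down. A row for reduction or discontinuation expects 5.0 / 5.0 / 2.5, understating toxicity at 100 mg. A row that also counts interruption expects 20p = 5.0 in every arm, provided each such toxicity leads at least to an interruption.

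**The case against.** Much of the other side's case stands, and it limits the point.

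- A reader might infer that the 100 mg arm must show zero reductions. The escalation provision rules this out: zero applies only while the subject is on 100 mg.
- A reader might infer that the split is fixed by the levels available and not by toxicity. Protocol Table 5-4 allows the same level, or leaves the choice to the investigator, for several events: Grade 4 neutropenia and thrombocytopenia, Grade 3 skin events, Grade 2 diarrhoea and other drug-related events. For Grade 3 hepatic events with direct bilirubin below Grade 3 it names the same level. Protocol 5.3.6.1 calls all of this guidance only. A few rows, such as Grade 3 diarrhoea, name only a lower level.
- A reader might take 4/20 against 0/20 as the size (a 20% rate in each arm). That needs every event to force a step down, none to recur, and every affected 100 mg subject to stop.
- A reader might infer that these tables bias dose selection. Protocol 3.2 bases the choice of regimen on pharmacodynamic, pharmacokinetic and anti-tumour data and does not name tolerability tables.

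The SAP is also descriptive throughout, names no tolerability comparison and plans no test. For scale, 5/20 against 1/20 has a two-sided Fisher p of 0.18. The high-level summary in SAP 7.1.6.1 shows the three actions together, and by-subject listings allow a combined count to be rebuilt.

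The summary rows cannot simply be added, though. With p = 25% and q = 0.5, reductions plus discontinuations come to 6.25, 7.5 and 5.0, although 5.0 distinct subjects are expected in each arm, because those who step down and later stop are counted twice.

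**Conclusion.** The point holds as a tendency in two descriptive rows. With equal toxicity, no reduction is possible while a subject is on 100 mg, and discontinuations tend to be higher at lower starting doses, so neither row alone compares tolerability fairly across the randomised doses. On the assumptions p = 25%, q = 0.5 and no escalation, expected discontinuations are about 1.25, 2.5 and 5.0 of 20 at 400, 200 and 100 mg, or half that if half resume at the same level. Only the arm size comes from the documents; p, q and s are assumptions.

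The overall TEAE, Grade 3 or higher, treatment-related and serious TEAE summaries do not depend on the dose levels, so toxicity itself is not hidden. Escalation leaves one further gap: the Safety Analysis Set groups by actual treatment (SAP 3.1.3), and the SAP does not say which dose column takes events after escalation. This is a worthwhile, inexpensive improvement and not a flaw in the main safety analysis. No dosing rule is questioned or proposed.

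**What to change.** In SAP 7.1.6.1, for the Table 3-2 columns:

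- Add one row for subjects with a TEAE leading to interruption, reduction or discontinuation of study drug, taking the first such action and counting each subject once, by randomised dose with an exact 95% CI (the method that Protocol 8.4.1 gives for binary variables).
- Count events up to any dose escalation and show post-escalation events separately, so that toxicity at a higher dose is not charged to the arm that started lower.
- Footnote the separate reduction and discontinuation rows: Protocol Table 5-3 has no level below 100 mg.
- State that this row groups by randomised dose and not by the actual treatment of the Safety Analysis Set.

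The row lessens the dependence on the dose levels without removing it entirely. For example, Table 5-4 lets dosing continue through Grade 4 neutropenia at the same or a lower level, so a reduction at 400 mg may have no counterpart at 100 mg.

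The cost is one more table row and a footnote. The actions are already needed for the planned summaries, and dosing rules, visits and data collection stay as they are.
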